9.3 Health economic outcomes

1. Health-related quality of life (EQ-5D-5L) (change from baseline to 4/ 26/ 52 weeks)
2. Use of healthcare resources and costs (measured at 26 and 52 weeks)
3. Cost-effectiveness based on cost per quitter and cost per Quality-Adjusted Life-Year (QALY) at 52 weeks, and modelled cost per QALY over patient lifetime

9.4 Lung health sub-study outcomes (subset of participants included in the cohort analysis only):

1. COPD Symptoms (change from baseline to 4/ 26/ 52 weeks) measured using COPD Assessment Test (CAT) and the Clinical COPD Questionnaire (CCQ)
2. Health-related quality of life (EQ-5D-5L) (change from baseline to 4/ 26/ 52 weeks)
3. Number of COPD exacerbations over the past 52 weeks (from baseline to 52 weeks)
4. Self-reported upper respiratory tract infections over the past 52 weeks (change from baseline to 52 weeks)

5. Post bronchodilator spirometry (FEV₁, FVC and MMEF change from baseline to 52 weeks)
 - Forced Expiratory Volume in 1 Second (FEV₁): The maximal volume of air that can be expired in the first second of a forced expiration from a position of full inspiration (measured in Litres (L) and also expressed as the % predicted for age, sex, height and race)
 - Forced Vital Capacity (FVC): The maximal volume of air that can be expired during a forced and complete expiration from a position of full inspiration (measured in L and % predicted)
 - Mean Mid-Expiratory Flow (MMEF): The average flow between 25% and 75% of the FVC manoeuvre (measured in L/sec and % predicted)
6. Full blood count (total and differential white blood cell (WBC) count x10⁹/L) (change from baseline to 52 weeks)
7. Serum/plasma biomarkers such as but not restricted to cytokines such as IL-6, IL-8, TNF- α ; antimicrobial peptides; and markers of proteinase activity (change from baseline to 52 weeks)
8. Toxicant analysis; to include toxicants such as formaldehyde, acetaldehyde, acrolein (change from baseline to 52 weeks)

9.5 Wellbeing sub-study outcomes (subset of participants included in the cohort analysis only):

1. Anxiety - Hospital Anxiety and Depression Scale (HADS) (change from baseline to 52 weeks)
2. Depression - HADS (change from baseline to 52 weeks)
3. Mixed anxiety and depression - EQ-5D-5L (change from baseline to 52 weeks)
4. Breathing related depression and social quality of life - CCQ (change from baseline to 52 weeks)

10. TRIAL PROCEDURES

10.1 Patient identification and invitation to participate

Potentially eligible patients will be identified and invited to take part in the trial (section 4).

10.2 Pre-baseline check

Patients who are interested in taking part in the trial will need to undergo a trial pre-baseline check (section 4.5). The pre-baseline check is conducted by a delegated member of site staff, BCTU trial office or QMUL trial team. If a patient fulfils the initial pre-baseline criteria (section 4.5.1), a baseline visit will be arranged to take place at the patient's local participating research site. This appointment must take place at least 12 weeks after any contraindication to spirometry. Once the baseline visit date/time is confirmed, the patient will be notified, i.e. verbally, appointment card, SMS text, email or letter.

10.3 Baseline visit

The baseline visit will occur face-to-face at a participating research site. At the start of the baseline visit, patients will have an opportunity to ask questions about the trial before being asked to provide full informed consent (section 5). Once consent is obtained, the patient will be screened against inclusion and exclusion criteria (section 6), which includes post bronchodilator

spirometry to check FEV1/FVC < 0.7 and to collect FEV1, FVC and MMEF values for outcome assessment. Site staff will complete the baseline CRF with participants, and participants will complete the baseline participant questionnaire, give an exhaled CO reading (section 10.9) and provide a blood sample (section 10.10). If a patient meets the eligibility criteria, as confirmed by a medically qualified doctor, and once all baseline measures have been collected, the patient will then be randomised into the trial (section 7). The research nurse will inform the participant of their randomised treatment allocation. Allocated products will be coordinated by a central stop smoking service as described in section 8. Participants will be given a £15 voucher to thank them for their time and will be reimbursed for their travel, and car parking as necessary.

10.4 Behavioural support telephone calls -1w, TDQ, +1w, +2w, +3w, +4w

Shortly after the baseline visit, participants will be contacted by telephone by the research team from the Health and Lifestyle Research Unit at the Wolfson Institute of Population Health at QMUL. During this call, the stop smoking advisor will deliver behavioural support following the standard treatment programme from the National Centre for Smoking Cessation Training.⁵⁷ Data collected during these calls, including all adverse events, will be recorded on specially designed CRFs. At the baseline visit, participants will be advised not to start their quit attempt until after the first behavioural support phone call (-1 week). However, if at the -1 week behavioural support telephone call, a participant has already started their quit attempt, the -1 week and TDQ phone call will be combined.

If a participant is unable to be contacted after 3 attempts, the QMUL trial team will send a letter/ email/ SMS text message. The participant will be asked to make contact with the QMUL team as soon as possible to collect the data for this time point. If no contact is established within 3 days of the call due date, this data will be considered missing for this follow up time point.

10.5 4-week follow up

In addition to the behavioural support offered at 4 weeks, a follow up questionnaire will be completed during the phone call carried out by the QMUL trial team. If a participant is unable to be contacted after 3 attempts, the QMUL trial team will send a 4-week minimum data collection (MDC) questionnaire, by post (paper) and/or email (with online link), to the participant. The participant will be asked to complete and return the questionnaire to the trial team at BCTU, in the format it was received. If no response is received within 14 days of follow up due date, this data will be considered missing for this follow up time point.

10.6 26-week follow up

The 26 week follow up call will be carried out by the Health and Lifestyle Research Unit, Wolfson Institute of Population Health, QMUL over the phone. During this call, the trial team will complete the 26-week CRF and follow up questionnaire with participants. If a participant is unable to be contacted after 3 attempts, the trial team will send the 26-week minimum data collection (MDC) questionnaire, by post (paper) and/or email (with online link), to the participant. The participant will be asked to complete and return the questionnaire to the trial team at BCTU, in the format it was received. If no response is received within 30 days of follow up due date, this data will be considered missing for this follow up time point.

10.7 52-week follow up

Participants will be contacted by the research site or trial team member to set up the 52 week follow up visit which will take place at the research site. This appointment must take place at least 12 weeks after any contraindication to spirometry. Once the follow-up visit date/time is confirmed, the patient will be notified, i.e. verbally, appointment card, SMS text, email or letter. At the 52-week visit, site staff will complete the 52-week CRF with participants, and participants

will complete a participant questionnaire, undergo spirometry to give FEV1, FVC and MMEF readings (section 10.8), give an exhaled CO reading (section 10.9) and provide a blood sample (section 10.10). Participants will be given a £15 voucher to thank them for their time and will be reimbursed for their travel, and car parking as necessary.

If a participant is unable to be contacted to arrange a 52-week follow up visit after 3 attempts, the trial team will send a letter or email to the participant. This letter/ email will remind the participant that their 52-week follow up is due and ask them to contact the trial office to arrange their follow-up visit.

If the participant makes no contact, after approximately 14 days of last contact attempt, the trial team will send a 52-week minimum data collection (MDC) questionnaire out to the participant. This will be sent either by post (paper) or email (with online link). The participant will be asked to complete and return the questionnaire to the trial team at BCTU, in the format it was received. If no response is received within 100 days of the 52-week follow up due date, this participant will be considered lost to follow-up and the data will be considered missing for this follow up time point.

10.8 Spirometry

Participants will be asked to undergo a spirometric assessment at the baseline visit and at the 52 week follow up visit. Post-bronchodilator spirometry will be undertaken according to ATS/ERS 2019 guidelines⁵⁸ and carried out by practitioners trained to ARTP or ERS Standard. FEV1, FVC and MMEF will be measured using a verified/calibrated spirometer.

A pragmatic approach will allow sites to use the spirometry equipment available. To minimise the variability, all sites will be asked to use lab/desktop spirometers and if possible, use the same equipment at the baseline and the 52-week follow up visits. Details of the spirometry equipment make, model and date last calibrated/ verified will be recorded on the relevant CRFs.

It is also anticipated that there could be between-technician variability. Spirometry will be undertaken by trained site staff, some of whom undertake this as part of usual care. The trial team will ask sites to delegate lung function testing to ARTP certified staff. If this is not feasible, the trial team will provide spirometry training modelled on the ARTP standard. This training will be provided by an experienced professional. During this training those trained will have their spirometry outputs checked to ensure they achieve the correct level of competence before being delegated this role for the trial. During the trial, quality checks will also be performed on a sample of spirometry results from each participating site.

10.9 Exhaled CO measurement

Participants will be asked to undergo assessment of exhaled CO levels at the baseline visit and at the 52 week follow up visit. Exhaled CO will be measured using a CO monitor and recorded as parts per million (ppm).

10.10 Collection and management of blood samples

Ideally between 36-45ml of blood will be collected from each participant at baseline and again at the 52 weeks follow up visit at the research sites. One EDTA tube will be used to conduct full blood following standard protocols. The remaining blood will be centrifuged for plasma/serum collection and storage. Samples will be maintained at -80 °C at the research sites. Sites unable to maintain samples at -80 °C may hold samples temporarily at -20 °C before shipping to the primary site (University of Birmingham Research Laboratories, Queen Elizabeth Hospital, Birmingham (QEHB)). Samples will be shipped to the primary site as capacity and storage conditions demands.

All samples will be shipped in a temperature-controlled environment on dry ice. Blood samples from participants who self-report quitting smoking and not vaping (quitters) or switching to exclusive e-cigarette use (vaping) will be sent to a contracted external laboratory to test cotinine levels. For participants who meet the inclusion criteria for the cohort analysis (based on smoking and vaping status) blood will be analysed for biomarkers and toxicants at the University of Birmingham or will be transported to contracted external laboratories for analysis.

Table 3: Schedule of Assessments

Visit	Identification of participants/ Pre-baseline assessment	Baseline	-1w pre TDQ	Target Quit day (TQD) + 3 days	+1 week post TQD ± 3 days	+2 week post TQD ± 3 days	+3 week post TQD ± 3 days	+4 week post TQD ± 14 days	26 week post TQD + 30 days	52 week post TQD + 100 days
Eligibility check	X	X								
Valid informed consent		X								
Concomitant medication check		X								
Relevant medical history taken		X								
Randomisation		X								
Dispensing of IMP (EC or Combination NRT)		X								
Behavioural support			X	X	X	X	X	X		
Instructions to patient about the trial		X								
Blood sample		X								X
Spirometry		X								X
Exhaled CO measurement		X								X
Baseline questionnaire*		X								
Behavioural support session questionnaire**								X		X
Follow up questionnaire***									X	X

*Baseline questionnaire includes the following validated questionnaires: COPD assessment test (CAT), Hospital anxiety and Depression Scale (HADS), Clinical COPD Questionnaire (CCQ) for measuring COPD symptoms., EQ-5D-5L for measuring quality of life for the economic evaluation., Fagerstrom Test for Nicotine Dependence (FTND).

**Behavioural support session questionnaire (at 4 weeks) includes the following questionnaires: Mood and physical symptom score (MPSS) for measuring nicotine withdrawal symptoms, COPD assessment test (CAT), Clinical COPD Questionnaire (CCQ) for measuring COPD symptoms and EQ-5D-5L† for measuring quality of life for the economic evaluation.

***Follow up questionnaire includes the following validated questionnaires: COPD assessment test (CAT) – 26w and 52w, Clinical COPD Questionnaire (CCQ) for measuring COPD symptoms - 26w and 52w, EQ-5D-5L for measuring quality of life for the economic evaluation – 26w and 52w, and Hospital anxiety and Depression Scale (HADS) – 52w only .

† Validated for delivery over the telephone

10.11 Withdrawal and changes in level of participation

Participants will be able to withdraw from the trial at any time. This will not put at risk their usual medical care for COPD. Failure to be contacted as part of the trial will not count as withdrawal from the trial. The only trial withdrawals will be the following:

- **No behavioural support calls:** The participant would no longer like to receive the behavioural support calls but is willing to be followed up in accordance with the schedule of assessments (i.e., the participant has agreed that data can continue to be collected and used in the trial analysis).
- **No further data collection:** The participant is not willing to be followed up in any way for the purposes of the trial AND does not wish for any further data to be collected (i.e., only data collected prior to any changes of levels in participation can be used in the trial analysis).

Participants are free to stop using the allocated intervention (ECs or NRT) at any time; the participant will not be withdrawn in these circumstance. In the event of a Serious Adverse Event (SAE) or Suspect Unexpected Serious Adverse Reaction (SUSAR) that is judged to be related to NRT or EC, the Chief Investigator (CI) will review the case and if deemed appropriate, the participant will be advised to stop using the medication.

The details of withdrawal should be clearly documented in a withdrawal form. Participants will be asked their reason for withdrawal, but it will be made clear that they are not obliged to give a reason.

In any case of withdrawal, participants will be offered standard care for smoking cessation as per local site protocol for COPD. Additionally, if a participant dies or is lost to follow-up during their participation in the trial, this should also be documented in the source documents and the trial team at BCTU should be notified.

The Trial Office will inform the research sites and QMUL if they are informed by a participant that they wish to withdraw from the trial and vice versa.

11. ADVERSE EVENT REPORTING

11.1 Definitions

Table 4: Adverse event reporting definitions

Severity Definitions	Mild	Awareness of signs or symptoms that do not interfere with the participant's usual activity or are transient and resolved without treatment and with no sequelae.
	Moderate	A sign or symptom, which interferes with the participant's usual activity.
	Severe	Incapacity with inability to do work or perform usual activities.
Adverse Event	AE	Any untoward medical occurrence in a participant administered a medicinal product and which does not necessarily have a causal relationship with this intervention. Comment: An AE can therefore be any unfavourable and unintended sign (including abnormal laboratory findings), symptom or disease temporally associated with the use of an investigational medicinal product, whether or not related to the investigational medicinal product.
Adverse Reaction	AR	All untoward and unintended responses to an IMP related to any dose administered. Comment: An AE judged by either the reporting Investigator or Sponsor as having causal relationship to the IMP qualifies as an AR. The expression reasonable causal relationship means to convey in general that there is evidence or argument to suggest a causal relationship.
Serious Adverse Event	SAE	Any untoward medical occurrence or effect that: Results in death Is life-threatening* Requires hospitalisation or prolongation of existing hospitalisation Results in persistent or significant disability or incapacity Is a congenital anomaly/birth defect Or is otherwise considered medically significant by the Investigator**
Serious Adverse Reaction	SAR	An AR which also meets the definition of a SAE.

Unexpected Adverse Reaction	UAR	An AR, the nature or severity of which is not consistent with the applicable product information (e.g., Investigator Brochure for an unapproved IMP or (compendium of) Summary of Product Characteristics (SmPC) for a licensed product). When the outcome of an AR is not consistent with the applicable product information the AR should be considered unexpected.
Suspected Unexpected Serious Adverse Reaction	SUSAR	A SAR that is unexpected i.e., the nature, or severity of the event is not consistent with the applicable product information. A SUSAR should meet the definition of an AR, UAR and SAR.

* The term life-threatening is defined as diseases or conditions where the likelihood of death is high unless the course of the disease is interrupted.

** Medical events that may not be immediately life-threatening or result in death or hospitalisation but may jeopardise the participant or may require intervention to prevent one of the other outcomes listed in the definitions above.

11.2 Adverse event recording – general

The recording and reporting of Adverse Events (AEs) will be in accordance with the UK Policy Framework for Health and Social Care Research, the Principles of Good Clinical Practice (GCP) as set out in the UK Statutory Instrument (2004/1031; and subsequent amendments) and the requirements of the Health Research Authority (HRA) and the Medicines for Human Use (Clinical Trials) Regulations 2004 and amendments thereof. Definitions for adverse event reporting are listed in Table 4: Adverse event reporting definitions in Section 11.1.

It is routine practice to record AEs in the participant's medical notes and it is also recommended that this includes the documentation of the assessment of severity and seriousness and of causality (relatedness) in relation to the intervention(s) in accordance with the protocol.

11.3 Adverse event reporting in the ECAL trial

The reporting period for AEs will be from randomisation until 26 weeks after agreed target quit day/ default target quit day. By this time point the trial supply of intervention product will have ended.

The safety profile for this trial population and interventions are well characterised so although the severity and causality of all AEs should be recorded in the patient's medical notes, a strategy of targeted reporting (to the sponsor) of AEs will not affect the safety of participants. Only the following AEs will be reported via the CRF completed during the scheduled follow up appointments and behavioural support calls:

- Rash/local skin irritation
- Nausea/vomiting
- Throat/mouth irritation
- Sleep disturbances
- Dizziness
- Headache
- Constipation

- Diarrhoea

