1.3.3 Justification for design

To definitively test the effectiveness and cost-effectiveness of EC for smoking cessation compared with NRT in COPD patients, a randomised controlled trial (RCT) is required with embedded economic analysis.

To investigate the effect of switching to vaping on lung health and wellbeing, a cohort analysis is necessary. For the cohort analysis, participants will be re-grouped based on their smoking and vaping status throughout the trial into vapers, quitters or smokers, rather than being analysed by trial arm. This is necessary as many people in each arm of the trial will relapse back to smoking, and therefore analysis by trial arm will not show the effect of vaping, quitting or smoking on lung health/wellbeing as trial arms will contain a mixture of these.

1.3.4 *Justification for choice of intervention*

We will be using a modern EC starter pack which will include an initial supply of e-liquid. There is no recommended length of use of ECs for smoking cessation as is the case for NRT where up to 12 weeks is recommended. Participants will therefore be given an initial supply of a sufficient amount to start using the EC (up to 20 mg nicotine/ml) and then advised to source continuing supplies. Participants will be advised how to continue sourcing supplies according to preference which may include changing devices, flavours and strengths as needed. This strategy was used successfully in our previous trials.^{30 55}

ECs will be compared with up to 12 weeks supply of combination NRT. Participants will be encouraged to use a nicotine patch in combination with a fast-acting product (e.g. gum, lozenge, microtab) as this has been shown to be the most effective way of using NRT⁵⁶ and is recommended by NICE.⁵⁴ Taking a pragmatic approach, should participants indicate they are not able to use the patch (e.g. due to previous reactions to nicotine patch), they will be able to choose two fast-acting products. Choice of fast-acting nicotine product for all participants will also be dependent on product availability.

1.3.5 *Justification of choice of primary outcome*

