3. TRIAL DESIGN AND SETTING

3.1 Trial design

The effectiveness and cost-effectiveness of ECs will be tested by conducting a national, multicentre, phase III, two arm RCT with internal pilot and economic evaluation. A target of 1250 participants will be recruited and randomised in a 1:1 ratio to either:

- Intervention (EC): EC Starter kit and initial supply of e-liquid; or
- Comparator (NRT): Up to 12 weeks of combination NRT (e.g., patch + oral product)

The trial includes two nested cohort studies assessing lung health and wellbeing.

The trial follow-up time points (and therefore outcome measures) will be established based on the TQD. If participants are unable to be contacted to set a TQD then a default TQD will be set (approximately 2 weeks after the baseline visit) for follow up time points to be based on. Participants will be followed up for 52 weeks post TQD.

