8. TRIAL INTERVENTION

8.1 Trial interventions and dosing schedule

Intervention arm: Electronic Cigarettes (EC) - Participants will receive an EC starter pack and an initial supply of e-liquid to start using the e-cigarette (up to 20 mg nicotine/ml). Participants will be advised on how to continue sourcing further supplies themselves from reputable vendors in their preferred nicotine strength and flavours. Participants in the intervention arm will be offered weekly telephone behavioural support up to 4 weeks post quit.

Comparator arm: Combination Nicotine Replacement Therapy (NRT) - Participants will receive up to 12-week supply of a nicotine patch plus a fast-acting nicotine product to be used in combination. A pragmatic approach to product allocation will allow for variation based on participant preference and availability. Participants who do not wish to use patches (e.g. due to previous experience of skin irritation) will be offered two types of fast acting product. Participants in the comparator arm will also be offered weekly telephone behavioural support up to 4 weeks post quit.

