8.1.1 Telephone behavioural support

All participants will be advised at the baseline visit that they will receive six weekly behavioural support telephone calls from stop smoking advisors which will commence within a few days of the baseline visit. These will be delivered by the Health and Lifestyle Research Unit at the Wolfson Institute of Population Health at Queen Mary University of London (QMUL). During these calls, the advisor will deliver behavioural support according to the National Centre for Smoking Cessation Training Standard Programme⁴⁴ including setting a TQD and providing further support around medication use. The TQD will be set for approximately 2 weeks after the baseline visit. Should participants have already started their quit attempt at the first phone call, the -1 week and TQD behavioural support phone calls will be combined. If participants are unable to be contacted to set a TQD then a default TQD will be set (approximately 2 weeks after the baseline visit) for follow up time points to be based on.

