9.2.2 Secondary outcomes

1. Abstinence from smoking for at least 26 weeks biochemically validated (exhaled CO < 8 ppm) at 52 weeks
2. 7-day point prevalence abstinence from smoking biochemically validated (exhaled CO < 8 ppm) at 52 weeks
3. Self-reported abstinence from smoking for at least 26 weeks at 52 weeks

-
4. Self-reported 7-day point prevalence abstinence from smoking at 4, 26 and 52 weeks
 5. Reduction in cigarettes smoked (self-report of any and > 50% reduction from baseline to 52 weeks, confirmed by reductions in expired CO readings at 52 weeks)
 6. Reduction in cigarettes smoked (self-report of any and > 50% reduction from baseline to 26/52 weeks)
 7. Continued use of allocated product at 4, 26 and 52 weeks
 8. Withdrawal symptoms and urges to smoke (change from baseline to 1/ 2/ 3/ 4 weeks) measured using the mood and physical symptom scale (MPSS)
 9. COPD Symptoms (change from baseline to 4/ 26/ 52 weeks) measured using COPD Assessment Test (CAT) and the Clinical COPD Questionnaire (CCQ)
 10. Number of COPD exacerbations over the past 52 weeks (from baseline to 52 weeks)
 11. Number of self-reported upper respiratory tract infections over the past 52 weeks (from baseline to 52 weeks)
 12. Post bronchodilator spirometry (FEV₁, FVC and MMEF change from baseline to 52 weeks)
 - Forced Expiratory Volume in 1 Second (FEV₁): The maximal volume of air that can be expired in the first second of a forced expiration from a position of full inspiration (measured in Litres (L) and also expressed as the % predicted for age, sex, height and race)
 - Forced Vital Capacity (FVC): The maximal volume of air that can be expired during a forced and complete expiration from a position of full inspiration (measured in L and % predicted)
 - Mean Mid-Expiratory Flow (MMEF): The average flow between 25% and 75% of the FVC manoeuvre (measured in L/sec and % predicted)

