11.4 Serious Adverse Event (SAE) reporting in ECAL trial

All adverse events which meet the definition of serious must be recorded in the participant medical notes, including the causality and severity. The reporting period for SAEs will be from randomisation until 26 weeks after agreed set target quit day/ default target quit day. When an SAE is identified during a scheduled telephone call with a participant, the trial team will notify the research site to investigate.

For all SAEs, the PI or delegate must do one of the following:

1. **Record safety reporting-exempt SAEs** in the medical notes but **not report** them to the trials office on an SAE form as per Section 11.4.1 Serious Adverse Events not requiring reporting to the Trial Office.
2. **Report SAEs to the trial office in a non-expedited manner.** This can only be done for the pre-defined subset of SAEs as per Section 11.4.2 Serious Adverse Events requiring non-expedited reporting to the Trial Office.
3. **Report SAEs to the trial office in an expedited manner** (within 24 hours of the site research team becoming aware of the event). All SAEs not covered by the above 2 categories must be reported as per Section 11.4.3 SAE Reporting process.

Note: when an SAE occurs at the same site at which the participant is receiving a trial product or is being followed up for trial purposes, processes must be in place to make the trial team at the site aware of any SAEs, regardless of which department first becomes aware of the event, in an expedited manner.

In addition, any SAE reported to the trial team by the participant will be passed to the PI to ensure the SAE is noted in the participant's medical notes. Where the SAE requires causality assessment, we will follow up with the PI until resolution of the SAE.

11.4.1 *Serious Adverse Events not requiring reporting to the Trial Office*

Safety reporting exempt SAEs must be recorded in the participant medical notes, including the causality and severity, but for trial purposes these events do not require reporting on the SAE CRF. The following will be considered as safety reporting exempt SAEs:

1. Pre-planned elective hospitalisation for any reason
2. Congenital anomalies or birth defects in the offspring of participants

11.4.2 *Serious Adverse Events requiring non-expedited reporting to the Trial Office*

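### SAE reporting stops 26 weeks after the quit date, so about 48% of follow-up has no routine SAE reporting; the one reason given, end of trial supply, fits NRT but not e-cigarettes

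*Protocol*

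**What the plan says.** Section 11.3 sets the AE window: "The reporting period for AEs will be from randomisation until 26 weeks after agreed target quit day/ default target quit day". It adds one reason: "By this time point the trial supply of intervention product will have ended". Section 11.4 sets the same window for serious events, without giving a reason: "The reporting period for SAEs will be from randomisation until 26 weeks after agreed set target quit day/ default target quit day".

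Follow-up is longer. Section 3.1 states: "Participants will be followed up for 52 weeks post TQD".

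On the interventions, section 8.1 gives the NRT arm at most 12 weeks of product. The EC arm gets a starter pack and a first supply of liquid, after which "Participants will be advised on how to continue sourcing further supplies themselves from reputable vendors". Section 1.3.4 explains why: "There is no recommended length of use of ECs for smoking cessation". Section 9.2.2 lists as a secondary outcome "Continued use of allocated product at 4, 26 and 52 weeks". Section 3.3 sorts participants, on status assessed at 52 weeks, into vapers, smokers and quitters for the lung health and wellbeing sub-studies.

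**The concern.** A safety window tied to the end of supply makes sense when exposure stops with the supply. That is roughly true of NRT here. For ECs the supplied product is only a start: further use at the participant's own cost is advised and measured. The end of trial supply therefore does not mark the end of EC exposure under the protocol's own design, and section 11.3 does not fit sections 1.3.4, 3.3, 8.1 and 9.2.2.

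What is at stake is the comparison of serious events. Section 1.2 says that no EC trial has yet been done in people with COPD, and the sub-studies are about sustained vaping. If serious events are reported only to week 26, any statement that they were similar between arms covers the first part of follow-up and leaves out the period in which longer-term vaping would be seen.

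**Working it through.** The protocol gives no figure for the share of follow-up that lies outside SAE reporting, so there is none to reproduce.

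**Inputs**
- End of AE and SAE reporting: week 26 after TQD (sections 11.3, 11.4).
- End of follow-up: week 52 after TQD (section 3.1), with a visit window of up to +100 days (Table 3).
- Randomisation to TQD: about 2 weeks, since randomisation takes place at the baseline visit and "The TQD will be set for approximately 2 weeks after the baseline visit" (section 8.1.1).
- Participants per arm: 625 (Trial Summary).
- Longest NRT supply: 12 weeks (section 8.1).

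**Share of follow-up without routine SAE reporting** = (52 − 26) / (lead-in + 52)
- Lead-in 2 weeks: 26/54 = 48.1%; the reported part is 28 weeks.
- Lead-in 1 week: 26/53 = 49.1%. Lead-in 3 weeks: 26/55 = 47.3%.
- Counted from TQD: 26/52 = 50%.
- Final visit at the end of its window: 100/7 = 14.3 weeks later, so (26 + 14.3)/(54 + 14.3) = 40.3/68.3 = 59%.

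**Person-time outside reporting**
- 625 × 26/52.18 = 311 person-years per arm, about 623 in both arms, before deaths and losses.

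**How the cut-off sits against each product**
- NRT: 26 − 12 = 14 weeks between the longest supply, if used from TQD, and the cut-off. The planned course lies inside the window.
- EC: no end date is set. The protocol does not say what share will still vape in weeks 27-52. If 20% to 60% did (an assumption), 311 × 0.20 to 311 × 0.60 gives about 62 to 187 person-years of EC use outside SAE reporting.

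**What is still captured after week 26**

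| Event | Route | Section |
|---|---|---|
| COPD exacerbations, upper respiratory infections | Secondary outcomes to week 52 | 9.2.2 |
| COPD-related admissions and emergency visits | Resource-use questionnaire at week 52, six-month recall | 16.2 |
| Deaths | Documented; trials unit notified | 10.11 |
| Other serious events, e.g. non-fatal cardiovascular events, cancers | Medical notes only; no stated routine report to the trial office | 11.4 |

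Nothing in the protocol extends SAE reporting past week 26. The last row is the gap.

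**The case against.** The strongest reply is that this is an open, risk-based choice. The trial is rated no riskier than standard care (section 3.4), the EC is a consumer product and not an investigational medicinal product (section 8.5.1), the cut-off is the same in both arms, and it is literally true that the supply from the trial has ended by week 26. All of that stands, but it does not explain the choice for ECs. Sections 10.11 and 11.5.2 already apply serious-event review to them, and supply is not exposure in that arm.

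Several stronger readings may tempt a reader, and the documents do not support them:
- *That SAE reporting stops because supply has ended.* The supply sentence is in section 11.3, on AEs. Section 11.4 gives no reason of its own.
- *That EC use is planned to run to week 52.* It is advised, permitted and measured, not required. Participants may stop at any time (section 10.11), and if use declines, more than half of actual exposure falls inside the window.
- *That nothing is known about serious events after week 26.* The table above shows partial capture.
- *That a late serious reaction would never reach the chief investigator or the DMC.* Section 10.11 puts no time limit on the chief investigator's review of related events, and section 11.4 passes participant-reported SAEs to the site investigator. What can be said is that no routine report is required.
- *That cardiovascular events, pneumonia and lung cancer lose an expedited causality review.* Section 11.4.2 puts them on the outcome CRF even inside the window. After week 26 they lose that report.
- *That ascertainment is unequal.* The gap is equally long in both arms. What differs is the exposure expected within it.
- *That a given number of SAEs or deaths goes unreported.* The protocol gives no SAE rate, and deaths are notified anyway.

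**Conclusion.** The point holds in a limited form. About 26 of 54 weeks (48%; 47% to 50% over the lead-ins shown and when counted from TQD) has no routine SAE reporting, about 311 person-years per arm if nobody died or was lost. The stated reason does not fit the EC arm. Serious events other than exacerbations, COPD-related admissions and deaths have no required routine report to the trial office in weeks 27-52, so the trial cannot compare serious events by arm over its full follow-up. The share rests only on the protocol's dates and the roughly two-week lead-in. The range for EC person-time rests on an assumed share of continuing users, and the conclusion does not depend on it. The primary outcome is untouched.

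**What to change.** Reconcile sections 11.3 and 11.4 with sections 1.3.4, 8.1, 9.2.2 and 10.11. Then:
- Collect serious events for weeks 27-52 in both arms on the existing 52-week CRF, or on the 52-week minimum data questionnaire where the visit is missed.
- Keep the events listed in section 11.4.2 on the outcome CRF as now, and let any other event judged related enter the existing SAE process.
- The 26-week limit may stay for the eight targeted AEs of section 11.3, but its supply-based reason should not be carried over to SAEs.

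The cost is a protocol amendment and some additional forms for sites. No new visit is needed. Participants who neither attend nor return the questionnaire would still be missed by this route, which should be stated when the results are reported.
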